7.3. Body Weight, Waist Circumference and Vital Signs

Descriptive statistics will be provided for the Safety Analysis Set by treatment group for body weight, BMI, waist circumference, and vital signs (systolic and diastolic blood pressures [mmHg], pulse [beats/min], respiration [breaths/min], and body temperature [$^{\circ}\text{C}$]), as follows:

- Baseline value

- Values at each postbaseline visit
- Change from baseline at each postbaseline visit
- Percent change from baseline (for weight and waist circumference only)

Change from baseline to a postbaseline visit will be defined as the postbaseline value minus the baseline value. Percent change from baseline will be defined as the change from baseline divided by the baseline value times 100 and displayed as percent (%).

Median (Q1, Q3) of the observed change from baseline values for body weight and waist circumference will be plotted by treatment group and visit. In the case of multiple values in an analysis window, data will be selected for analysis as described in Section 3.8.3. No formal statistical testing is planned.

A by-subject listing of vital signs will be provided by subject ID number and visit in chronological order. In the same manner, a by-subject listing of body weight, height, and BMI will be provided.

7.4. Prior and Concomitant Medications

Medications collected at screening and during the study will be coded using the current version of the World Health Organization (WHO) Drug dictionary.

7.4.1. Prior Medications

Prior medications are defined as any medication taken before a subject took the first study drug.

Prior medications will be summarized by Anatomical Therapeutic Chemical (ATC) drug class Level 4 and preferred name using the number and percentage of subjects for each treatment group and overall. A subject reporting the same medication more than once will be counted only once when calculating the number and percentage of subjects who received that medication. The summary will be ordered alphabetically by ATC medical class and then by preferred term in order of descending overall frequency within each ATC medical class. For drugs with the same frequency, sorting will be done alphabetically.

For the purposes of analysis, any medication with a start date prior to the first dosing date of study drug will be included in the prior medication summary regardless of when the stop date is. If a partial start date is entered the medication will be considered prior unless the month and year (if day is missing) or year (if day and month are missing) of the start date are after the first dosing date. Medications with a completely missing start date will be included in the prior medication summary, unless otherwise specified.

Summaries will be based on the Safety Analysis Set. No formal statistical testing is planned.

7.4.2. Concomitant Medications

Concomitant medications are defined as medications taken while a subject took study drug. Use of concomitant medications will be summarized by Anatomical Therapeutic Chemical (ATC) drug class Level 4 and preferred name using the number and percentage of subjects for each treatment group. A subject reporting the same medication more than once will be counted only once when calculating the number and percentage of subjects who received that medication. The summary will be ordered alphabetically by ATC medical class and then by preferred term in descending overall frequency within each ATC medical class. For drugs with the same frequency, sorting will be done alphabetically.

For the purposes of analysis, any medication with a start date prior to or on the first dosing date of study drug and continued to take after the first dosing date, or started after the first dosing date but prior to or on the last dosing date of study drug, will be considered concomitant medications. Medications started and stopped on the same day as the first dosing date or the last dosing date of study drug will also be considered concomitant. Medications with a stop date prior to the date of first dosing date of study drug or a start date after the last dosing date of study drug will be excluded from the concomitant medication summary. If a partial start date is entered, any medication with the month and year (if day is missing) or year (if day and month are missing) after the study drug stop date will be excluded from the concomitant medication summary. If a partial stop date is entered, any medication with the month and year (if day is missing) or year (if day and month are missing) prior to the date of first study drug administration will be excluded from the concomitant medication summary. Medications with completely missing start and stop dates will be included in the concomitant medication summary, unless otherwise specified. Summaries will be based on the Safety Analysis Set. No formal statistical testing is planned.

All prior and concomitant medications (other than per-protocol study drugs) will be provided in a by-subject listing sorted by subject ID number and administration date in chronological order.

7.5. Electrocardiogram Results

A shift table of the investigators' assessment of ECG results at Week 12 compared with baseline values will be presented by treatment group using the following categories: normal; abnormal, not clinically significant; abnormal, clinically significant; or missing. The number and percentage of subjects in each cross-classification group of the shift table will be presented. Subjects with a missing value at baseline or postbaseline will not be included in the denominator for percentage calculation. No inferential statistics will be provided.

A by-subject listing for ECG assessment results will be provided by subject ID number and visit in chronological order.

7.6. Other Safety Measures

A data listing will be provided for subjects experiencing pregnancy during the study.

7.7. Changes From Protocol-Specified Safety Analyses

[figure not shown]
There are no deviations from the protocol-specified safety analyses.

8. PHARMACOKINETIC ANALYSES

8.1. PK Sample Collection

[figure not shown]
A single PK blood sample will be collected at any time during each On-Treatment Visit for all subjects.

CCI

8.2. PK Analyses Related to Intensive PK Sampling

CCI

Concentrations of GS-0976 and its metabolites in plasma will be determined using validated bioanalytical assays.

8.2.1. Estimation of PK Parameters

Pharmacokinetic parameters will be estimated using Phoenix WinNonlin® software using standard noncompartmental methods. The linear up/log down rule will be used in conjunction with the appropriate noncompartmental model, with input values for dose level, dosing time, plasma concentration, and corresponding real-time values, based on drug dosing times whenever possible.

All predose sample times before time zero will be converted to 0.

For area under the curve (AUC), samples BLQ of the bioanalytical assays occurring prior to the achievement of the first quantifiable concentration will be assigned a concentration value of 0 to prevent overestimation of the initial AUC. Samples that are BLQ at all other time points will be treated as missing data in WinNonlin. The nominal time point for a key event or dosing interval (τ) may be used to permit direct calculation of AUC over specific time intervals. The appropriateness of this approach will be assessed by the PK scientist on a profile-by-profile basis.

Pharmacokinetic parameters such as AUC_{tau} , λ_z , and $t_{1/2}$ are dependent on an accurate estimation of the terminal elimination phase of drug. The appropriateness of calculating these parameters will be evaluated upon inspection of PK data on a profile-by-profile basis by the PK scientist.

8.2.2. PK Parameters

Pharmacokinetic parameters will be generated for all subjects in the PK Substudy Analysis Set. For each subject, the following PK parameters will be calculated for GS-0976 and its metabolites as appropriate to evaluate the PK objectives of the study.

Table 8-1. Study Treatments and Associated Analytes

Treatment	Analyte
GS-0976 20 mg tablet	GS-0976, GS-834773, and others as appropriate
GS-0976 5 mg tablet	GS-0976, GS-834773, and others as appropriate

Table 8-2. PK Parameters for Each Analyte

Analyte	Parameters
GS-0976	AUC _{last} , AUC _{tau} , C _{max} , T _{max} , C _{last} , T _{last} , C _{tau} , λz, CLss/F, and t _{1/2}
GS-834773	AUC _{last} , AUC _{tau} , C _{max} , T _{max} , C _{last} , T _{last} , C _{tau} , λz, and t _{1/2}

Individual subject concentration data and individual subject PK parameters for GS-0976 and its metabolites will be listed and summarized using descriptive statistics by treatment. Summary statistics (n, mean, SD, coefficient of variation [%CV], median, min, max, Q1, and Q3) will be presented for both individual subject concentration data and individual subject PK parameters by time point and by treatment. Moreover, the geometric mean, 95% CI, and the mean and SD of the natural log-transformed values will be presented for individual subject PK parameter data.

Individual concentration data listings and summaries will include all subjects with concentration data. The sample size for each time point will be based on the number of subjects with nonmissing concentration data at that time point. The number of subjects with concentration BLQ will be presented for each time point. For summary statistics, BLQ values will be treated as 0 at predose and imputed to one-half of the lower limit of quantitation (LLOQ) for postdose time points.

Individual PK parameter data listings and summaries will include all subjects for whom PK parameter(s) can be derived. The sample size for each PK parameter will be based on the number of subjects with nonmissing data for that PK parameter.

The following tables will be provided for each analyte by treatment for the PK Substudy:

CCI

CCI

Individual and mean postdose concentration values that are \leq LLOQ will not be displayed in the figures and remaining points connected.

The following listings will be provided:

- PK sampling details by subject including actual dosing time and actual draw time, calculated time postdose of sample collection, differences in scheduled and actual draw times, sample age, and sample concentration
- Individual data on determination of plasma half-life and corresponding correlation coefficient

10. SOFTWARE

SAS® Software Version 9.X. SAS Institute Inc., Cary, NC, USA.

11. SAP REVISION

Revision Date (DD MMM YYYY)	Section	Summary of Revision	Reason for Revision

12. APPENDIX

Appendix 1. Procedures Table for Study GS-US-426-3989

Assessments	Screening ^a	Baseline / Day 1	On-treatment Visits				Follow-Up Visit ^b (± 5 Days)
			Week 1 ± 3 days	Week 4 ± 3 days	Week 8 ± 3 days	Week 12/ET ^b ± 7 days	
Clinical Assessments							
Written Informed Consent ^c	X						
Determine Eligibility	X	X					
Medical History	X						
Physical Examination	X	X ^d	X ^d	X ^d	X ^d	X ^d	X ^d
Vital Signs ^e including Weight	X	X	X	X	X	X	X
Height	X						
Waist Circumference		X				X	
12- lead ECG	X	X				X	
Ultrasound ^f	X						
MRE, MRI-PDFF	X					X	
FibroScan ^{®g}		X				X	
SF-36, WPAI, and CLDQ Questionnaires ^h		X				X	
Adverse Events	X	X	X	X	X	X	X
Concomitant Medications	X	X	X	X	X	X	X
Dispense Study Drugs		X		X	X		
Review of Study Drug Dosing Compliance (Pill Count)			X	X	X	X	
Laboratory Assessments							
Subject Fasting ⁱ	X	X	X	X	X	X	X

Assessments	Screening ^a	Baseline / Day 1	On-treatment Visits				Follow-Up Visit ^b (± 5 Days)
			Week 1 ± 3 days	Week 4 ± 3 days	Week 8 ± 3 days	Week 12/ET ^b ± 7 days	
Chemistry, Hematology, Coagulation Panel	X	X	X	X	X	X	X
Lipid Profile		X	X	X	X	X	X
Pregnancy Test ^j	X	X		X	X	X	X
Serum FSH ^k	X						
Single PK Sampling			X	X	X	X	
Hemoglobin A1c	X	X				X	
Blood and Urine Collection (Biomarker)		X	X	X		X	
Stool Collection (Biomarker)		X				X	
Urine Drug Screening ^l	X						
HIV-1, HBV & HCV ^m Serology	X						
CCI							
Genomic Sample ⁿ		X					

a Screening assessments to be completed within 4 weeks prior to Day 1. The Screening period also may be extended longer under special circumstances with the explicit approval of the Gilead Medical Monitor.

b Subjects discontinuing treatment at any time for any reason (Early Termination – ET) should complete the procedures listed for the Week 12/ET visit AND the Follow-Up visit.

c Obtain written informed consent before initiation of any screening procedure.

d Symptom-driven physical examination

e Vital signs include blood pressure, heart rate, respiration rate, and body temperature.

f Ultrasound may be performed if necessary to confirm NAFLD.

g Perform FibroScan® if available.

h It is recommended that QoL questionnaires be completed prior to any study procedures being performed and prior to the subject seeing a health care provider. Refer to the Study Reference Binder for guidance on QoL questionnaire administration for subjects with QoL questionnaires available at Baseline/Day 1.

i Subjects must be in a fasted state at least 8 hours prior to blood collection.

j Females of childbearing potential only (See [Appendix 3](#) in protocol). Serum pregnancy test at Screening and urine pregnancy test at all other visits, except Week 1.

k **CCI**

l Drug screen for amphetamines, cocaine, and opiates (i.e., heroin, morphine).

m HCV Ab positive, reflex to HCV RNA.

n **CCI**

Appendix 2. Pooled Cohort Risk Score and Pooled Cohort Risk Calculation

No.	Parameters	Coefficient			
		Female		Male	
		White or Other	African America	White or Other	African America
1	Ln Age (y)	-29.799	17.114	12.344	2.469
2	Ln Age, Squared	4.884	N/A	N/A	N/A
3	Ln Total Cholesterol (mg/dL)	13.540	0.940	11.853	0.302
4	Ln Age × Ln Total Cholesterol	-3.114	N/A	-2.664	N/A
5	Ln HDL-C (mg/dL)	-13.578	-18.920	-7.990	-0.307
6	Ln Age × Ln HDL-C	3.149	4.475	1.769	N/A
7	Ln Treated Systolic BP (mm Hg)	2.019	29.291	1.797	1.916
8	Ln Age × Ln Treated Systolic BP	N/A	-6.432	N/A	N/A
9	Ln Untreated Systolic BP (mm Hg)	1.957	27.820	1.764	1.809
10	Ln Age × Ln Untreated Systolic BP	N/A	-6.087	N/A	N/A
11	Current Smoker (1=Yes, 0=No)	7.574	0.691	7.837	0.549
12	Ln Age × Current Smoker	-1.665	N/A	-1.795	N/A
13	Diabetes (1=Yes, 0=No)	0.661	0.874	0.658	0.645

A	Baseline Survival	0.9665	0.9533	0.9144	0.8954
B	Individual Sum = $\sum(\text{coefficient} \times \text{parameter})$	For each individual patient, individual sum is summation of product of each parameter and its corresponding coefficient for that sex-race group for all parameters listed above (#1 -#13). Note: N/A indicates that the specific coefficient is not available thus the corresponding parameter will not be included in calculation.			
C	Group Wise Mean Sum of (Coefficient × parameter)	Equal to the [sum of individual sum of all patients in sex- and race- specific group] divided by the [total number of patients in that sex- and race- specific group].	-29.18	86.61	61.18
D	Pooled Cohort Risk Score	= B – C = Individual Sum - Group Wise Mean Sum of (Coefficient × parameter)			19.54
E	Pooled Cohort Risk =Estimated probability of a first hard ASCVD event within 10 years *	= 1 - A \wedge exp(B-C) = 1 - Baseline Survival \wedge exp (Individual Sum- Group wise mean sum)			

* ASCVD = atherosclerotic cardiovascular disease; BP = blood pressure; HDL-C = high-density lipoprotein cholesterol; Ln = natural logarithm. Age is the actual age when the lab parameters are collected for the visit.. Total Cholesterol and HDL-C, Systolic BP are assessed at visit when risk score are collected. Smoker, Diabetes and status of hypertension treatment are collected at Screening/Baseline. Round Pooled Cohort Risk Score to 0.001. The lab parameters need to be measured from the same blood draw.

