6.2.2. Statistical Analysis Methods

For exploratory efficacy endpoints, the number and percentage of subjects in each category will be presented for categorical variables. Descriptive statistics (n, mean, SD, median, Q1, Q3, minimum, and maximum) will be provided for continuous exploratory efficacy variables by treatment group, as follows:

- Baseline values
- Values at each postbaseline visit
- Change from baseline at each postbaseline visit
- Percent change from baseline at each postbaseline (except for pooled cohort risk score)

Change from baseline at a postbaseline visit will be defined as the visit value minus the baseline value. Percent change from baseline will be defined as (the visit value – the baseline value)/the baseline value $\times 100\%$. The mean, median, Q1, Q3, minimum, and maximum will be displayed to the same reported number of digits, and SD will be reported to the number of digits plus 1.

For continuous exploratory efficacy endpoints, mean (SD) of the observed change from baseline values will be plotted using a line plot by treatment group and visit.

Listings of all exploratory efficacy endpoints will be provided.

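### SAP Appendix 2 row C defines the pooled cohort centring term both as a patient mean and as printed constants; using a trial mean would misstate absolute cardiovascular risk

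*SAP*

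**What the plan says.** SAP Appendix 2 builds the score in five rows.

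- Row A gives a fixed baseline survival for each sex and race column: 0.9665, 0.9533, 0.9144, 0.8954.
- Row B is the individual sum of coefficient times parameter.
- Row C is the group mean. In words, its numerator is the "sum of individual sum of all patients in sex- and race- specific group" and it is "divided by the [total number of patients in that sex- and race- specific group". The same row prints -29.18, 86.61 and 61.18. A fourth value, 19.54, sits one row lower in the text available for review; I treat that as table displacement and read it as the fourth column of row C.
- Row D sets the score to "Individual Sum - Group Wise Mean Sum", that is, B - C.
- Row E sets the risk to 1 minus A raised to the power "exp (Individual Sum- Group wise mean sum".

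The Appendix 2 footnote takes age, total cholesterol, HDL-C and systolic pressure at each visit, and fixes smoking, diabetes and hypertension treatment at Screening/Baseline. Table 3-1 gives score and risk visit windows from Baseline to Week 12. Section 6.2.2 summarises values and change from baseline by treatment group, and makes one exception: "Percent change from baseline at each postbaseline (except for pooled cohort risk score".

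**The concern.** A mean over trial patients and a printed constant are different quantities, and rows D and E need exactly one of them. The mean is written as a complete sentence, so the conflict is not an artefact of text extraction. Row B uses the word patient for the person being scored, so reading row C as this trial's patients is natural. Two programmers could both follow row C and report different risks.

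The absolute risk level is at stake, because row E pairs C with a fixed baseline survival. So may be the planned by-arm changes from baseline, depending on when a mean is taken.

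**Working it through.** **Inputs.** The coefficients and rows A to E are from SAP Appendix 2; the 2:2:1 allocation is from SAP Section 1.2.1. Patient values are assumptions, stated where used.

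**The printed constants.** They cannot be recomputed, because the data behind them are not in the documents. A scale check is possible. For an assumed profile (age 55, total cholesterol 213, HDL-C 50, untreated systolic pressure 120, non-smoker, no diabetes), row B gives -29.68, 86.17, 60.70 and 18.97. Each is within 0.6 of its constant, which supports placing 19.54 in the fourth column.

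**Change in score, D = B - C, under three readings of C.**

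1. Printed constants: change in D = change in B.
2. Trial mean at baseline, held fixed: change in D = change in B. Nothing is lost on the score scale.
3. Trial mean recomputed at each visit: change in D = change in B minus the group's mean change in B. The average over the group is exactly 0.

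**Absolute risk (readings 2 and 3).** A patient whose B equals the trial mean has B - C = 0, so risk = 1 - A^exp(0) = 1 - A. Under reading 2 this applies at baseline, under reading 3 at every visit. Compare an assumed patient with age 55, total cholesterol 190, HDL-C 42, treated systolic pressure 132, diabetes and no smoking:

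| Group | B - C with constant | Risk with constant | 1 - A |
|---|---|---|---|
| Women, White/Other | 0.700 | 6.6% | 3.35% |
| Women, African American | 1.255 | 15.5% | 4.67% |
| Men, White/Other | 0.529 | 14.1% | 8.56% |
| Men, African American | 0.792 | 21.6% | 10.46% |

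For example, White/Other women: 1 - 0.9665^exp(0.700) = 1 - 0.9665^2.014 = 6.6%. If the trial group averaged this profile, trial-mean centring would report 3.35%.

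Averaged over simulated patients (age about 55, total cholesterol 195, HDL-C 42, systolic pressure 132, half diabetic; spreads, smoking and treatment rates also assumed), mean baseline risk with the constants against a trial mean is:

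- White/Other women: 7.3% against 4.9%
- White/Other men: 13.6% against 11.9%
- African American women: 11.9% against 6.6%
- African American men: 15.3% against 12.3%

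**Within-arm change (reading 3 only).** Suppose cholesterol rises 10% and HDL-C falls 5% on active drug, with no change on placebo. For a White/Other man aged 55 (ln 55 = 4.007), the change in B is

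(11.853 - 2.664 × 4.007) × ln 1.10 + (-7.990 + 1.769 × 4.007) × ln 0.95 = 0.112 + 0.046 = 0.158.

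At 2:2:1, 80% of an average group is on active drug, so the group mean change is 0.8 × 0.158 = 0.127. Centring then gives active 0.158 - 0.127 = +0.03 and placebo 0 - 0.127 = -0.13. The difference is still 0.158.

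On the risk scale, simulated White/Other men show:

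| Centring | Active | Placebo | Difference (points) |
|---|---|---|---|
| Printed constants | +1.7 | 0 | +1.70 |
| Mean at each visit | about 0 | -1.3 | +1.35 |

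In White/Other women the difference goes from +0.84 to +0.51.

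**All four groups together.** In 400 simulated trials of 125 patients (assumed sex and race mix, cholesterol down 15% on both active arms only), the 20 mg minus placebo score difference was -0.184 with the constants and -0.181 with visit means. The corresponding risk differences were -1.15 and -1.08 points, and -0.99 with a baseline trial mean held fixed.

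**The case against.** The strongest reply is that row C never says trial or study patients. The sentence may only explain where the constants came from, with the constants being the values to use. They stand in sex and race columns alongside fixed baseline survivals, and the SAP cites the published risk guideline. That reading is credible and may be what the programmers would do. But the SAP does not say so, and the sentence taken literally is a different rule, so the ambiguity stands.

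A reader might go further and infer that the formula removes any change over time in cardiovascular risk, or could hide or reverse a harm. The documents do not support this, for three reasons.

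- Row C names no visit. A trial mean held from baseline leaves score change intact.
- The groups are defined by sex and race, not by arm. Even with visit-specific means, active and placebo patients in a group lose the same amount and their score difference is unchanged. A wrong direction appears only if the placebo arm is ignored.
- The lipid signal in Protocol Sections 1.2.5.2 and 1.4 is raised triglycerides, which are not among the 13 score inputs. Graded hypertriglyceridemia and high cholesterol are assessed separately under SAP Section 7.2.2 and Appendix 4.

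The public SAP redacts the efficacy endpoint and model text (Sections 6.1 and 6.2.1), so how the score enters any comparison there cannot be checked.

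**Conclusion.** The point holds in a limited form. Row C carries two rules for one term, and the SAP does not choose between them.

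- **Any trial mean.** Absolute risk is centred on 1 - A. Under the assumed inputs this understates mean baseline risk by 7.3 - 4.9 = 2.4 points in White/Other women and 13.6 - 11.9 = 1.7 points in White/Other men. That a trial group at its mean gets 1 - A is exact; the point differences depend on the assumed patient mix.
- **A mean recomputed at each visit.** This is an added assumption, not SAP text. Average score change per sex and race group becomes zero, an active arm's shift shrinks by about 80%, and placebo shows a spurious opposite shift. The between-arm score difference is exact within a group and nearly so overall. The risk difference is attenuated but keeps its direction.

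The endpoint is exploratory, Section 3.5 plans no formal testing, and the primary safety and tolerability objective is not affected. I have high confidence that the two rules conflict as written, and only moderate confidence that anyone would apply the trial mean.

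**What to change.** In SAP Appendix 2 row C, state that C is the printed constant for the patient's sex and race column and is used unchanged at every visit: -29.18 (female, White or Other), 86.61 (female, African American), 61.18 (male, White or Other), 19.54 (male, African American). Check that the four values line up with their columns in the source table. Delete the patient-mean sentence, or relabel it as a description of how the constants were derived.

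This is a one-line text correction. It needs no new data and changes no other analysis. If programs already exist, confirm that they use the constants.

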### 4.2. Inclusion Criteria

Subjects must meet *all* of the following inclusion criteria to be eligible for participation in this study.

- 1) Males and females between 18-75 years of age; inclusive based on the date of the Screening visit;
- 2) Willing and able to give informed consent prior to any study specific procedures being performed;
- 3) Meets the following conditions:
  - a) A clinical diagnosis of NAFLD with imaging or a liver biopsy documenting fatty liver within two years prior to Screening (if necessary, an ultrasound may be performed during Screening to confirm NAFLD), and
  - b) Screening MRI-PDFF with  $\geq 8\%$  steatosis, and
  - c) Screening MRE with liver stiffness  $\geq 2.5$  kPa.

Note: criterion 3a. must be met before evaluating criteria 3b. and 3c.

OR

- d) A historical liver biopsy within 12 months of Screening consistent with NASH (defined as the presence of steatosis, lobular inflammation, and hepatocellular ballooning) with fibrosis, but not cirrhosis, and
  - e) No documented weight loss  $> 5\%$  between the date of the liver biopsy and Screening.
- 4) Platelet count  $\geq 100,000/\text{mm}^3$
- 5) Creatinine Clearance (CLCr) as calculated by the Cockcroft-Gault equation  $\geq 60$  ml/min
- 6) Female subjects of childbearing potential (see definition in [Appendix 3](#)) must have a negative serum pregnancy test prior to starting study treatment;
- 7) All female subjects of childbearing potential who engage in heterosexual intercourse must agree to use a highly effective method of contraception during intercourse from the Screening visit throughout the study period and for 30 days following the last dose of study drugs (see [Appendix 3](#) for details);

- 8) Male subjects are required to use barrier contraception (condom plus spermicide) during intercourse from the Screening through the study completion and for 90 days following the last dose of study drugs (see [Appendix 3](#) for details);
- 9) Male subjects must refrain from sperm donation from Screening through at least 90 days following the last dose of study drugs.
- 10) Female subjects must refrain from egg donation or harvest for 30 days after last dose of study drugs.
- 11) Willing and able to comply with scheduled visits, drug administration plan, laboratory tests, other study procedures, and study restrictions.
- 12) Must be able to read and complete Quality of Life questionnaires independently.

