- 16) Unstable cardiovascular disease as defined by any of the following:
  - a) Unstable angina within 6 months prior to Screening
  - b) Myocardial infarction, coronary artery bypass graft surgery or coronary angioplasty within 6 months prior to Screening
  - c) Transient ischemic attack or cerebrovascular accident within 6 months prior to Screening
  - d) Obstructive valvular heart disease or hypertrophic cardiomyopathy
  - e) Congestive heart failure;
- 17) Use of prohibited concomitant medications as described in Section 5.4
- 18) History of a malignancy within 5 years prior to Screening with the following exceptions:
  - a) Adequately treated carcinoma in situ of the cervix
  - b) Adequately treated basal or squamous cell cancer or other localized non-melanoma skin cancer;
- 19) Any laboratory abnormality or condition that, in the investigator's opinion, could adversely affect the safety of the subject or impair the assessment of study results;
- 20) Participation in another investigational study of a drug or device within 28 days prior or within 5 half-lives of the prior investigational agent (whichever is longer) prior to Screening;
- 21) Concurrent participation in another therapeutic clinical study;

- 22) Known hypersensitivity to GS-0976, the metabolites, or formulation excipient;
- 23) Presence of any condition that could, in the opinion of the investigator, compromise the subject's ability to participate in the study, such as history of substance abuse or a psychiatric (including any subjects with a psychiatric hospital admission or emergency room visit in the 2 years prior to Screening) or medical condition;
- 24) Unavailable for follow-up assessment or concern for subject's compliance with the protocol procedures;
- 25) Contraindications or inability to complete MRI scanning (e.g. presence of permanent pacemakers, implanted cardiac devices, weight restrictions, etc.).

Subjects with laboratory abnormalities outside of the above parameters may be approved for inclusion in the trial with approval from the Medical Monitor.

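### SAP Appendix 2 scores a 10-year first-event cardiovascular risk with no visible age or prior-event limit; it does not apply to prior-event subjects, and in young White/Other women it rises as age falls (minor, exploratory)

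*SAP*

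**What the plan says.** SAP Appendix 2, row E, labels the output as the "Estimated probability of a first hard ASCVD event within 10 years". Row B describes the calculation: "For each individual patient, individual sum is summation of product of each parameter and its corresponding coefficient for that sex-race group". The footnote fixes the age input: "Age is the actual age when the lab parameters are collected for the visit". No minimum age and no condition on cardiovascular history appears in the appendix.

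Protocol 4.2, criterion 1, admits "Males and females between 18-75 years of age; inclusive based on the date of the Screening visit". Protocol 4.3, criterion 16, excludes "Myocardial infarction, coronary artery bypass graft surgery or coronary angioplasty within 6 months prior to Screening" and "Transient ischemic attack or cerebrovascular accident within 6 months prior to Screening". The same events more than 6 months before Screening are not excluded by these items.

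The score and risk have analysis visit windows in SAP Table 3-1. SAP 6.2.2 names the pooled cohort risk score among the continuous exploratory variables, which are summarised by visit with mean, SD, median and quartiles. SAP 3.6.2 keeps all data and plans no outlier sensitivity analysis. SAP 5.3 says that general medical history is listed but not coded. SAP 6.1, 6.1.1 and 6.2.1 and Protocol 8.1.3 are redacted.

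**The concern.** Two separate questions arise. The first is definition. A subject who had an infarction a year before Screening cannot have a first event in the next 10 years. Appendix 2 would still return a value, and that value would be averaged with the others under the first-event label.

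The second is the shape of the equation at young ages. The White/Other female column is quadratic in ln(age), with a negative linear and a positive squared coefficient. Such a curve has a minimum, and below it a younger woman receives a higher risk. If the minimum lies inside the enrolled range of 18 to 75, the reported risk is implausible for women below it.

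At stake is how an exploratory cardiovascular-risk table reads for a drug whose lipid effects the sponsor intends to monitor closely (Protocol 1.3.1).

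**Working it through.** The plan gives no worked risk value, so there is no stated figure to reproduce. All coefficients below are from SAP Appendix 2. The lipid and blood pressure values are my assumptions.

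**Formula.** Risk = 1 − A^exp(B − C). For White/Other women A = 0.9665 and C = −29.18. The text extraction shifts row C, so I assigned its four constants (−29.18, 86.61, 61.18, 19.54) to the columns in order. For an untreated, non-diabetic woman:

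B = −29.799 ln(age) + 4.884 ln(age)² + 13.540 ln(TC) − 3.114 ln(age) ln(TC) − 13.578 ln(HDL) + 3.149 ln(age) ln(HDL) + 1.957 ln(SBP) + smoker × (7.574 − 1.665 ln(age))

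**Example: smoker, TC 200, HDL-C 45, untreated SBP 125.**

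- Age 20: B = −89.270 + 43.831 + 71.739 − 49.426 − 51.687 + 35.910 + 9.449 + 2.586 = −26.87. B − C = 2.31, exp(2.31) = 10.1, and risk = 1 − 0.9665^10.1 = 29.1%.
- Age 40: B = −109.925 + 66.461 + 71.739 − 60.863 − 51.687 + 44.219 + 9.449 + 1.432 = −29.17. B − C = 0.01, and risk = 3.4%.

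| Age | Smoker | Non-smoker |
|---|---|---|
| 20 | 29.1% | 2.6% |
| 25 | 9.4% | 1.1% |
| 30 | 4.9% | 0.74% |
| 40 | 3.4% | 0.82% |
| 50 | 4.3% | 1.5% |

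**Turning age.** Setting the derivative of B in ln(age) to zero gives

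age = exp[(29.799 + 3.114 ln(TC) − 3.149 ln(HDL) + 1.665 × smoker) / 9.768]

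- TC 200, HDL-C 45, non-smoker: exp(34.311/9.768) = 33.5 years.
- The same, smoker: exp(35.976/9.768) = 39.8 years.
- TC 180–240 and HDL-C 40–50: 31.3 (non-smoker) to 43.8 (smoker).
- TC 160–280 and HDL-C 35–60: 28.5–40.5 for non-smokers, 33.8–48.0 for smokers.

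C is constant within a sex-race group, so the reversal and its turning age do not depend on how row C is read. Only the risk levels do.

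**The other three columns.** These have no squared term, so the sign of the age slope settles the direction.

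- African American women: 17.114 + 4.475 ln(HDL) − 6.087 ln(SBP) untreated, or − 6.432 ln(SBP) treated. Over HDL-C 30–60 and SBP 110–180 it is negative only for treated SBP 160 or more with HDL-C 30, or treated SBP 180 with HDL-C 35 or less.
- White/Other men: 12.344 − 2.664 ln(TC) + 1.769 ln(HDL) − 1.795 × smoker. It is positive at every value tried; the smallest was 0.64, at TC 350 and HDL-C 25 in a smoker.
- African American men: +2.469 throughout.

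**Effect on a group mean.** Replacing one 40-year-old smoker by a 20-year-old with the same values in an arm of 25 shifts the mean by (29.1 − 3.4)/25 = 1.03 percentage points.

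**Prior events.** This part needs no arithmetic. Row E defines a first event, criterion 16 looks back only 6 months, and nothing in the visible text removes the subjects in between.

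**The case against.** The strongest reply is that the definition of this endpoint and its model are redacted, and a restriction by age or history may be stated there. Row B's wording about each patient explains how a sum is formed and is not clearly a statement of population. This stands. The finding is about the visible text, and a reader should not infer that every enrolled subject is certainly scored.

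Other tempting inferences also go too far:

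- **Young women in general.** The reversal belongs to one column. African American women at ordinary values, and men at every value tried, run in the expected direction.
- **Impossible or undefined output.** The formula always returns a value between 0 and 1. For a prior-event subject it is mislabelled; for a 20-year-old smoker it is implausible.
- **A few subjects dominating the mean.** With the same lipids and blood pressure, a 70-year-old White/Other diabetic male non-smoker scores about 32%, above the 20-year-old smoker. A non-smoking 20-year-old woman scores 2.6%, below a non-smoking woman of 60 (3.6%). SAP 6.2.2 also reports medians and quartiles.
- **Distorted change scores.** The weight on ln(TC) is 4.21 at age 20 and 2.05 at 40, but it keeps falling to 0.79 at 60, so the decline alone is not a defect. Age barely moves in 12 weeks.
- **A cut at exactly 40.** No passage gives that age, and the turning points straddle it.

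What survives is that Appendix 2, followed as written, gives a first-event risk to people who have had the event, and a wrong age direction in one subgroup.

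**Conclusion.** The point holds as a minor one. In the visible text the score has no prior-event restriction, although eligibility admits events older than 6 months. It also has no age bound, although the White/Other female coefficients reverse below about 31 to 44 years at the assumed TC 180–240 and HDL-C 40–50.

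The size is modest: about 1 percentage point on a 25-subject arm mean for one young smoker, and less for a non-smoker. The documents do not give the number of young White/Other women, smokers or prior-event subjects, so the actual effect could be nil.

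It would be wrong to infer that a trial conclusion is at risk. The primary endpoint is safety (Protocol 8.1.2), efficacy is exploratory without formal comparisons (Protocol 8.5), and any p-values are exploratory (SAP 3.5). The risk levels rest on the printed constants in row C. The conclusion on scope rests on the redacted sections containing no restriction.

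**What to change.** In Appendix 2:

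1. Compute the score and risk only for subjects with no prior MI, stroke, TIA or coronary revascularisation. Because history is not coded, flag these events by blinded review of the medical history listing before database finalization.
2. Prespecify a lower age bound for the summary, chosen by the sponsor from the equation's validated range or from the turning ages above. About 40 would remove most of the reversal but not all of it: at TC 240, HDL-C 40 and untreated SBP 125, a smoker still falls from 6.1% at 40 to 5.9% at 44. As a minimum, add a sensitivity summary that excludes White/Other women below the chosen age.
3. Report by arm how many subjects are set to missing and why.

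If the redacted sections already restrict the population, a cross-reference in Appendix 2 is enough. Eligibility does not change.

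The cost is fewer subjects in one exploratory table and a short blinded history review. A single bound for all four columns also drops younger men and African American women, whose risk runs in the expected direction at ordinary values; the sensitivity summary avoids that loss. Under SAP section 1, a change after SAP finalization must be documented in the CSR.
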